1.4.1 Pharmacokinetics/Pharmacodynamics

1.4.1.1 Animal Models of Efficacy

As with all β -lactams that target penicillin-binding proteins, the controlling PD parameter for cefiderocol is the percentage of the dosing interval for which the free-drug concentration in plasma exceeds the minimum inhibitory concentration ($\%fT_{>MIC}$), and while the plasma PK measurements can determine the drug exposure over time, corrected for protein binding, the MIC remains the key variable in determining $\%fT_{>MIC}$.

Shionogi has conducted a series of studies in animal models of infection, including urinary tract (murine), thigh (murine), and lung (murine and rat). In addition to the dose fractionation used in the murine models, the rat lung model was designed to reproduce human drug exposure, including infusion times of 1 and 3 hours (Figure 1-2).

Figure 1-2 Efficacy of Cefiderocol (Human 3- and 1-hr Infusion of 2 g IV q8h) Compared with Meropenem (Human 1 g IV q8h) Against *K. pneumoniae* VA-384 in a Respiratory Tract Infection Model in Cannulated Rats

cfu = colony-forming units; hr = hour; IV = intravenous; MIC = minimum inhibitory concentration; NTC = nontreatment control; q8h = every 8 hours

The results of the curative effect of the drug on carbapenem-resistant rat lung infections were better with a 3-hour infusion than a 1-hour infusion (for additional information refer to the current IB).

The pharmacokinetic/pharmacodynamic (PK/PD) parameter required for efficacy was determined in a murine thigh model of infection caused by 16 strains of Gram-negative bacteria with widely divergent MICs. The %*f*_{T>MIC} values of cefiderocol required for a static effect and 1-log₁₀ reduction were approximately 60% to 70% and 70% to 80%, respectively. The %*f*_{T>MIC} values required for efficacy were similar among bacterial species (for additional information refer to the current IB).

In summary, the nonclinical data support the clinical development of cefiderocol as a potential human therapeutic agent against serious bacterial infections. The target PK/PD parameter is 70% to 80% of time during which plasma concentrations are above the mean inhibitory concentration (*f*_{T>MIC}).

1.5 Clinical Experience

1.5.1 Phase 1

The safety and tolerability of cefiderocol has been assessed in a total of 212 healthy adult subjects who participated in 6 clinical pharmacology studies (a single- and multiple-ascending dose study [Study 1203R2111], an intrapulmonary PK study [Study 1214R2112], a renal impairment study [Study 1222R2113], a mass balance study [Study 1516R2114], a thorough QT [TQT]/corrected QT [TQT_c] study [Study 1603R2116], and a 3-part drug interaction study [Study 1521R2115]). In these studies, healthy adult subjects or subjects with impaired renal function received single doses of cefiderocol ranging from 100 to 4000 mg (4 g) or multiple doses of up to 2000 mg (2 g) for up to 10 days, infused intravenously over 1 or 3 hours. In general, cefiderocol was safe and well tolerated in the clinical pharmacology studies. There were no treatment-related or dose-dependent trends in vital sign measurements, electrocardiogram/electrocardiography (ECG) parameters, or clinical laboratory test results. There were no deaths or serious adverse events (SAEs) reported in any study. Adverse events (AEs) occurred relatively infrequently, were mostly mild in severity, and almost all resolved spontaneously without intervention. There were no dose-dependent trends in the frequency or type of AEs reported.

Cefiderocol is primarily excreted unchanged (approximately 90%) in the urine (Study 1516R2114), has a plasma half-life of 2.75 hours, and is associated with linear PK in the therapeutic dose range with little accumulation after multiple-dose administration. After administration of single 100- to 2000-mg (2 g) doses, infused over 1 hour (single ascending dose study [Study 1203R2111]) and single 2- to 4-g doses, infused over 3 hours TQT_c study (Study 1603R2116), the C_{max} and AUC of cefiderocol increased in proportion to the dose. After administration of multiple 2-g doses of cefiderocol every 8 hours (q8h) infused over 1 hour (once daily doses on Days 1 and 10 and q8h doses from Days 2 to 9), only a slight accumulation (1.05- to 1.16-fold) for the C_{max} and AUC of cefiderocol was observed, and plasma concentrations of cefiderocol reached steady state within 1 day of repeated administration (Study 1203R2111). After administration of a single 1000-mg (1-g) dose of [¹⁴C]-cefiderocol, cefiderocol was the major component in plasma, accounting for 92.27% of the plasma AUC for total radioactivity. A degradation product, pyrrolidine chlorobenzamide, accounted for 4.70% of the plasma AUC for plasma total radioactivity, with all other metabolites each accounting for < 2% of the plasma AUC for plasma total radioactivity (Study 1516R2114). The majority (98.6%) of total radioactivity was excreted unchanged in urine, with negligible amounts (2.8%) excreted in feces (Study 1516R2114).

A Phase 1 study to assess the repolarization effects of cefiderocol on the human heart was conducted as a TQT_c study (Study 1603R2116) in accordance with the International Council for Harmonisation of Technical Requirements for Pharmaceuticals for Human Use (ICH) E14 Guidance and subsequent Questions & Answers. The first part of the study consisted of a sequential-group safety and tolerability study in which the safety of the suprathreshold dose of cefiderocol was confirmed. The second part of the study consisted of a TQT_c study in which single 2-g (therapeutic) and 4-g (suprathreshold)

doses of cefiderocol administered as 3-hour infusions were assessed along with placebo (to cefiderocol) and moxifloxacin (active control) in a double-blind, crossover design in a total of 48 subjects.

The point estimates of the least squares (LS) means of baseline and placebo-corrected QTc intervals ($\Delta\Delta\text{QTcF}$) calculated using Fridericia's correction for the 2- and the 4-g doses of cefiderocol were < 5 msec and the upper bounds of the 1-sided 95% CI were < 10 msec at all postinitiation of the infusion time points. For the moxifloxacin treatment, a prolongation of Fridericia's corrected QT (QTcF) interval was observed for all time points from 1 to 10 hours postdose, confirming that a positive effect on the QTcF interval could be detected in the study (the lower bound of 1-sided 95% CI of LS means in the $\Delta\Delta\text{QTcF} > 5$ msec). The results indicate that single 2- and 4-g doses of cefiderocol did not prolong the $\Delta\Delta\text{QTcF}$ interval to a level of regulatory concern and met the criteria stipulated in the ICH E14 guideline associated with a negative TQT study ([Study 1603R2116](#)).

1.5.2 Phase 2 and Phase 3

1.5.2.1 Phase 2 Complicated Urinary Tract Infections

A Phase 2 study of the safety and efficacy of cefiderocol administered at a 2-g dose over a 1- hour infusion to 300 subjects with complicated urinary tract infections (cUTIs) has been completed ([Study 1409R2121](#)). The results support the safety profile of cefiderocol in a subject population using the same dose (2 g, q8h) proposed for this study.

1.5.2.2 Phase 3

A pathogen-based, Phase 3 study in subjects with evidence of carbapenem resistance, Gram-negative infections at various infection sites (CREDIBLE-CR, [Study 1424R2131](#)) and a Phase 3 study in subjects with pneumonia (APEKS-NP, [Study 1615R2132](#)) are currently on-going.

Refer to the current IB for additional details of completed studies.

2. STUDY OBJECTIVES

2.1 Primary Objectives

The primary objectives of this study are:

- To estimate the concentration of cefiderocol in ELF, at steady state in hospitalized subjects with known or suspected bacterial pneumonia being treated with standard of care (SOC) antibiotics and requiring mechanical ventilation
- To estimate the ratio of the concentration for cefiderocol in ELF relative to plasma ($R_{C,EP}$) in hospitalized subjects with known or suspected bacterial pneumonia on treatment with SOC antibiotics and requiring mechanical ventilation

3. INVESTIGATIONAL PLAN

3.1 Overall Study Design and Plan

This is a multicenter, single-arm, open-label study to assess the intrapulmonary and plasma concentrations of cefiderocol at steady state after multiple-dose administration in hospitalized subjects with known or suspected bacterial pneumonia on treatment with SOC antibiotics and requiring mechanical ventilation.

Screening of subjects will occur within 48 hours prior to administration of the first dose of cefiderocol on Day 1 of the study. A minimum of 3 (and up to approximately 18) qualified subjects will receive an initial 2-g dose (or renally adjusted dose) of cefiderocol on Day 1 (within 72 hours of the start of potentially effective treatment with SOC antibiotics for bacterial pneumonia) and subsequently receive cefiderocol q8h (or q6h if subject has augmented renal function) with the dosage specified in Table 3-1.

Table 3-1 Cefiderocol Dosing and Bronchoalveolar Lavage Procedure for Various Degrees of Renal Function

Creatinine Clearance	Dosage	Number of Doses Prior to Performing BAL
Augmented renal function (CrCl \geq 120 mL/min) ^a	2 g, q6h, 3-hour infusion	3-6 doses
Normal renal function (CrCl < 120 mL/min) ^a	2 g, q8h, 3-hour infusion	3-6 doses
Mild renal impairment (CrCl 60 to < 90 mL/min) ^a	2 g, q8h, 3-hour infusion	3-6 doses
Moderate renal impairment (CrCl 30 to < 60 mL/min) ^a	1.5 g, q8h, 3-hour infusion	3-6 doses
Severe renal impairment (CrCl 15 to < 30 mL/min) ^a	1 g, q8h, 3-hour infusion	6-9 doses

BAL = bronchoalveolar lavage; CrCl = creatinine clearance; q8h = every 8 hours; q6h = every 6 hours

^a Creatinine clearance will be calculated by Cockcroft-Gault equation at Screening.

The dose of cefiderocol administered to each subject will be determined by the investigator based on dosing recommendations (see [Section 5.2](#)). End of Treatment (EOT) assessments will occur within 24 hours after administration of the last dose of cefiderocol, or at early termination. The End of Study (EOS) visit will occur 7 days (\pm 3 days) if there is no SAE, after administration of the last dose of cefiderocol. For both cases EOS visit can be performed on-site or by telephone (see [Table 3-2](#)). If an SAE is observed it must be reported to Safety and all SAEs, regardless of causality, will be followed until resolution, stabilization, the condition becomes chronic, or the subject is lost to follow-up. The investigator will make an effort to collect AEs for 7 days after the last dose of study drug.

One ELF sample for determination of cefiderocol concentrations will be collected by bronchoalveolar lavage (BAL) procedure at 3, 5, or 7 hours, depending on the ELF cefiderocol concentration data obtained, after administration of at least 3 doses of

cefiderocol in subjects with normal or augmented renal function and subjects with mild or moderate renal impairment and after administration of at least 6 doses of cefiderocol in subjects with severe renal impairment. In addition, data from any BAL procedures performed during the study as part of routine patient care will also be collected as part of study data. A total of 4 blood samples for determination of plasma cefiderocol concentrations will be collected at prespecified time points corresponding to the dose after which the ELF sample is collected. Ongoing PK assessment of concentration data from both ELF and plasma samples will be performed for every 3 subjects to determine if modifications of the ELF sampling time point in subsequent subjects are needed. All revised sampling time point modifications will be provided by the sponsor, discussed with the investigator, and documented (see [Section 7.5](#)).

Blood and ELF samples will be collected also for determination of urea concentration. Urea is used as an endogenous marker of ELF because urea is small and relatively nonpolar and can travel across membranes freely to reach the outer surfaces of alveoli. The concentration of urea in ELF is considered to be same as the serum urea concentration, implying complete distribution. Therefore, the calculated volume of ELF (V_{ELF}) is adjusted for excess exogenous volume using the concentration of urea in blood and ELF (see [Section 7.6.4.1.3](#)).

Safety assessments including physical examinations, vital sign measurements, and clinical laboratory tests will be performed at prespecified time points prior to, during, and after administration of cefiderocol. In addition, data will be captured at various time points during the study from safety assessments (physical examinations, vital sign measurements, chest X-rays, and clinical laboratory tests) performed as part of routine patient care (see [Section 7.5.2.1](#)), date and result will be entered in the source documents and the electronic case report form (eCRF). Adverse events will be monitored throughout the study from the time informed consent is obtained until 7 days after administration of the last dose of cefiderocol if there are no SAEs.

Table 3-2 Study Schematic

Screening	Cefiderocol Administration	End of Treatment	End of Study Visit ^a
Within 48 hours prior to the administration of the first dose of cefiderocol	
Minimum of 3 doses (up to a total of 6 doses) in subjects with normal renal function and subjects with mild or moderate renal impairment, q8h; and with augmented renal function, q6h
 
Minimum of 6 doses (up to a total of 9 doses) in subjects with severe renal impairment, q8h
 
Initial dose must be within 72 hours of the start of treatment with SOC antibiotics for bacterial pneumonia
	Within 24 hours after administration of the last dose of cefiderocol or early termination	7 days (\pm 3 days) after administration of the last dose of cefiderocol

q8h = every 8 hours; q6h = every 6 hours; SOC = standard of care

a End of Study Visit can be performed on-site or by telephone

3.2 Rationale for Study Design and Control Group

This study is an open-label, multicenter, single-arm study and is being conducted to estimate the degree of penetration of cefiderocol into infected lung tissue, as measured by plasma and ELF cefiderocol concentrations.

The study will be conducted in an open-label (unblinded) manner considering that the primary purpose of the study is focused on PK parameter assessments, which are objective rather than subjective endpoints and therefore do not require blinding for unbiased interpretation. Accordingly, no control group is necessary to achieve the study objectives.

The 2-g dose (or renally-adjusted dose) of cefiderocol infused intravenously over 3 hours, selected for the proposed study is the anticipated therapeutic dose of cefiderocol. Furthermore, 3 doses of cefiderocol in subjects with normal or augmented renal function and subjects with mild or moderate renal impairment, and 6 doses of cefiderocol in subjects with severe renal impairment will be administered in order to achieve steady state at the time the primary study assessments are performed. The recommended blood sampling scheme for determination of plasma cefiderocol concentrations provides a collection interval that will allow the PK profiles for cefiderocol to be adequately characterized. The ELF sample, along with a blood sample, will initially be obtained at the time point where cefiderocol is expected to achieve C_{max} .

The study population consists of subjects with known or suspected bacterial pneumonia. Currently, the available concentration data for cefiderocol in ELF, a surrogate for lung tissue penetration, is in healthy subjects where approximately 24% plasma unbound concentrations were measured in ELF. However, the ELF data determined in healthy subjects may not be representative of the degree of penetration in patients with infected

lungs due to a variety of considerations including alterations in blood flow and degree of penetrability resulting from thickened secretions.

A minimum of 3 subjects will be enrolled to provide a summary of cefiderocol concentrations in ELF in hospitalized subjects with known or suspected bacterial pneumonia being treated with SOC antibiotics and requiring mechanical ventilation. However, if necessary, up to approximately 18 subjects may be enrolled to ensure adequate information is obtained to meet the objectives of this study. Nonevaluable subjects will be replaced. See [Section 7.5.2](#) for more details.

3.3 Study Duration

3.3.1 Study Duration in Individual Subjects

The maximum duration of study participation for an individual subject, from the time of Screening (within 48 hours prior to the administration of the first dose of cefiderocol) to the EOS visit (up to 7 days after administration of the last dose of cefiderocol), is 13 days. Cefiderocol dosing will be terminated once the BAL procedure has been performed and ELF samples, plasma PK samples, and urea samples have been collected for analyses at which time no further cefiderocol dosing will be permitted.

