5.2 Treatments to be Administered

The dose of cefiderocol administered to each subject will be determined based on renal function as described in this section (see [Table 5-1](#)). Dosing recommendations for subjects with moderate or severe renal impairment and subjects with augmented renal clearance are provided. For all subjects serum creatinine levels should be checked once daily to determine whether dose adjustments of cefiderocol should be made.

Beginning on Day 1, subjects will be administered 2-g doses (or renally adjusted dose) of cefiderocol infused intravenously over 3 hours, q8h (or q6h for subjects with augmented renal function), for an expected minimum of 3 doses and up to a total of 6 doses in subjects with normal or augmented renal function and subjects with mild or moderate renal impairment, and for an expected minimum of 6 doses and up to a total of 9 doses in subjects with severe renal impairment. Cefiderocol dosing will be terminated once the BAL procedure has been performed and ELF samples, plasma PK samples, and urea samples have been collected for analyses at which time no further cefiderocol dosing will be permitted. After initiation of cefiderocol administration, doses of cefiderocol administered to each subject may be adjusted based on changes in renal function as assessed daily by CrCl (using the Cockcroft-Gault equation) and according to the dosing recommendations for subjects (see [Table 5-1](#)). Any dosing modifications based on the dosing recommendations will be agreed to by the investigator and documented. Please see the Renal Function and Dose Adjustment Log in the pharmacy manual.

Table 5-1 Dosing Recommendations of Cefiderocol Based on Renal Function

Creatinine Clearance	Dosage
Augmented renal function (CrCl \geq 120 mL/min) ^a	2 g, q6h, 3-hour infusion
Normal renal function (CrCl < 120 mL/min) ^a	2 g, q8h, 3-hour infusion
Mild renal impairment (CrCl 60 to < 90 mL/min) ^a	2 g, q8h, 3-hour infusion
Moderate renal impairment (CrCl 30 to < 60 mL/min) ^a	1.5 g, q8h, 3-hour infusion
Severe renal impairment (CrCl 15 to < 30 mL/min) ^a	1 g, q8h, 3-hour infusion

CrCl = creatinine clearance; q6h = every 6 hours; q8h = every 8 hours

a Creatinine clearance will be calculated by Cockcroft-Gault equation at Screening.

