7.5 Pharmacokinetics Assessments

Pharmacokinetic assessments will be performed for plasma and ELF samples obtained from each subject. The ELF and plasma sample collections must be done in connection with the same cefiderocol infusion. Detailed procedures for sample collection, handling, labeling, storage, and shipment to the bioanalytical laboratory will be provided by the sponsor in study-specific laboratory manual(s). Please see [Appendix 2](#) of the protocol for more details on PK and urea sampling.

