7.5.1 Plasma Samples

A total of 4 blood samples for determination of plasma cefiderocol concentrations will be collected at prespecified time points after administration of at least 3 doses of cefiderocol in subjects with normal or augmented renal function and subjects with mild or moderate renal impairment, and after administration of at least 6 doses of cefiderocol in subjects with severe renal impairment: (1) 1 hour after the start of infusion, (2) 3 hours after the start of infusion (within 30 minutes prior to the end of infusion), (3) 2 hours after the end of infusion (within \pm 1 hour), and (4) 4 hours after the end of infusion (within \pm 1 hour). The plasma PK samples will be collected at time points around the same cefiderocol infusion that the BAL procedure is performed. A blood sample for urea assessment will be collected as part of plasma sample collection within 30 minutes prior to the BAL procedure.

For each blood sample collected, the actual sampling time will be recorded in the source documents and the eCRF.

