7.8 Allowable Time Window

Measurements will be performed according to the Time and Events Schedule in [Appendix 1](#), and the acceptable time deviations relative to the time points are specified in [Table 7-2](#) below. Every effort should be made to adhere as closely as possible to procedure time points specified.

Table 7-2 Allowable Time Window

Study Activity	Specified Time or Day	Acceptable Time Window
Blood sample collection at 1 hour after the start of infusion for PK		± 15 minutes
ELF and blood sample collection at 3 hours after the start of infusion for PK		Within 30 minutes prior to the end of infusion
ELF and blood sample collection at 2 hours or 4 hours after the end of infusion for PK		± 1 hour
Blood sample collection corresponding with ELF sample collection for PK		± 5 minutes after ELF sample collection
Safety assessments		± 1 hour
EOT assessments	24 hours after the last dose of cefiderocol	+ 1 day
EOS visit	7 days after the last dose of cefiderocol	± 3 days

ELF = epithelial lining fluid; EOS = End of Study; EOT = End of Treatment; PK = pharmacokinetic(s)

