Scenario 3: The next set of subjects enrolled (3 additional) will undergo BAL procedure 4 hours after the end of infusion as well as plasma PK and urea assessments in ELF and serum

	3rd dose of cefiderocol (or subsequent dose) ^a			
	1 hr after start of infusion	3 hrs after start of infusion	2 hrs after end of infusion	4 hrs after end of infusion
Plasma PK	X	X	X	X
Serum Urea ^b				X
BAL PK and Urea				X

BAL = bronchoalveolar lavage; hrs = hour(s); PK= pharmacokinetic

After the third scenario, sponsor may decide to enroll up to nine additional subjects and the timing of the BAL procedure will be determined based on the information collected from the initial 9 subjects (Scenario 1-3).

*a) 6th dose for subjects with severe renal impairment

*b) A blood sample collection for urea together with PK analysis will be performed within 30 minutes prior to the start of the BAL procedure

PK results (blood and ELF) will be reviewed by Sponsor promptly after the first 3 subjects to determine if modifications of the ELF sampling time need to be adjusted for subsequent subjects enrolled. The CRO (Syneos Health) will inform the investigator and research staff of any sampling time adjustments promptly after the sponsor review and determination. The investigator will be required to confirm receipt of the adjustment information via email or other written document as appropriate.

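### For the rare q6h subjects sampled at dose 3, 4 or 5, nothing holds the infusion due at 6 h, so the last plasma sample and a late BAL can fall inside it

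*Protocol*

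**What the plan says.** Protocol Table 3-1 gives augmented renal function (CrCl 120 mL/min or more) "2 g, q6h, 3-hour infusion". Sections 7.5.1 and 7.8 and Appendix 2 require four plasma samples from every subject, the last "4 hours after the end of infusion". Table 7-2 allows ±1 h for "ELF and blood sample collection at 2 hours or 4 hours after the end of infusion for PK". Scenario 3 in Appendix 2 has subjects "undergo BAL procedure 4 hours after the end of infusion", with no exception for q6h. SAP 8.1 adds an ELF time that the protocol does not have: 3 h after the end of infusion, ±1 h.

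On stopping, Protocol 3.3.1 says "Cefiderocol dosing will be terminated once the BAL procedure has been performed and ELF samples, plasma PK samples, and urea samples have been collected". Protocol 5.2 and SAP 2.2 and 3.5 repeat the rule.

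Two other provisions bear on the matter. Dosing is planned "for an expected minimum of 3 doses and up to a total of 6 doses in subjects with normal or augmented renal function" (Protocol 5.2), with BAL at the 3rd dose or, if that is inconvenient, the 4th, 5th or 6th. Protocol 7.5 adds: "The ELF and plasma sample collections must be done in connection with the same cefiderocol infusion". Appendix 1, footnote m, expects q6h dosing to be rare.

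**The concern.** The stop rule takes effect when the last sample has been drawn. For a q6h subject the next infusion falls due before that, even if the BAL was done at 3 or 5 h, because the 7 h plasma sample is still to come. A site that follows the schedule and the stop rule literally would start another infusion at 6 h.

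A 7 h plasma value would then no longer describe the sampled dose. It would still be inside its window, so the SAP 8.4.1 provision on samples far outside the windows would not remove it; only the discretionary exclusion of anomalous values could. Otherwise it enters the nominal-time summary and the mean plasma and ELF plot that SAP 8.4.3 pools over regimens.

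ELF concentration and the ELF-to-plasma ratio, the subjects of the two primary objectives, are exposed when a q6h subject has a late BAL: at 7 h, or at the additional SAP 8.1 time.

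**Working it through.** **Clock times, from the start of the sampled infusion.** A 3 h infusion plus 0, 2 or 4 h gives 3, 5 and 7 h, which reproduces the protocol's stated ELF times. The SAP 8.1 addition is 3 + 3 = 6 h.

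| Sample | Window | Share inside the next q6h infusion (6–9 h) | Share inside the next q8h infusion (8–11 h) |
|---|---|---|---|
| 3 h | 2.5–3 h | none | none |
| 5 h | 4–6 h | none (touches at 6 h) | none |
| 6 h (SAP 8.1, ELF only) | 5–7 h | half | none |
| 7 h | 6–8 h | all | none (touches at 8 h) |

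The overlap is therefore specific to q6h. It needs sampling at dose 3, 4 or 5, because the cap of 6 rules out a further dose after dose 6.

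**Size in plasma.** The model is one-compartment superposition. Protocol 1.5.1 says the drug "has a plasma half-life of 2.75 hours", so k = ln 2 / 2.75 = 0.2521 per hour. The shorter half-life of 2.0 h is an assumption for augmented clearance. In units of infusion rate/(k × volume), with sampling at dose 3:

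- Held-dose value at time t: (1 − e^(−3k)) × e^(−k(t−3)) × (1 + e^(−6k) + e^(−12k)).
- Added by an infusion started at 6 h: 1 − e^(−k(t−6)).
- At 7 h: held 0.5305 × 0.3649 × 1.2690 = 0.2456; added 0.2228; factor (0.2456 + 0.2228)/0.2456 = 1.91.
- At 8 h: held 0.5305 × 0.2836 × 1.2690 = 0.1909; added 0.3960; factor (0.1909 + 0.3960)/0.1909 = 3.07.
- At 6 h and 6.5 h the factors are 1.00 and 1.42. At steady state those for 7 h and 8 h are 1.90 and 3.05.
- At a half-life of 2.0 h the factors for 7 h and 8 h are 2.59 and 4.84.

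**Shift in the 7 h plasma mean from one affected subject.** The other subjects are on 2 g q8h, also at dose 3, with a 7 h value of 0.5305 × 0.3649 × (1 + e^(−8k) + e^(−16k)) = 0.2228. The relative rise is 0.2228 / [0.2456 + (N − 1) × 0.2228].

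- N = 18: 0.2228/4.0332 = 5.5%.
- N = 9: 0.2228/2.0280 = 11.0%.
- N = 3: 0.2228/0.6912 = 32%, which applies only if the whole study ends after three subjects, since every subject gives a 7 h plasma sample.
- Geometric mean: 1.907^(1/18) = 1.037 and 1.907^(1/9) = 1.074, that is 4% and 7%.
- With 2.0 h for the q6h subject and 2.75 h for the others (equal volume assumed), both means rise by 5% and 11% for N = 18 and 9.

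**Range for the ratio of one q6h subject with a late BAL.** If ELF tracks plasma, the ratio is unchanged. If ELF has not responded at all, it falls by the reciprocal of the plasma factor:

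| Time of BAL | Half-life 2.75 h | Half-life 2.0 h (assumed) |
|---|---|---|
| 7 h | 1/1.91 = 0.52 | 1/2.59 = 0.39 |
| 8 h | 1/3.07 = 0.33 | 1/4.84 = 0.21 |

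For the SAP 8.1 time the limit at 2.75 h runs from 1.00 at 6 h through 1/1.42 = 0.70 at 6.5 h to 0.52 at 7 h.

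**Illustration for the mean ratio.** Take one value at 0.52 of its held-dose level and the others equal to that level. With 3 subjects in the cell the mean is (0.52 + 2)/3 = 0.84, a fall of 16%. With 12 (3 from Scenario 3 plus all 9 optional subjects) it is (0.52 + 11)/12 = 0.96, a fall of 4%.

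**The case against.** The strongest reply is that the documents already treat the sampled dose as the last. The dose totals match the permitted BAL doses in every renal category: 3 to 6 doses with BAL at dose 3 to 6, and 6 to 9 with BAL at dose 6 to 9. If a q6h subject sampled at dose 3 were given the 6 h dose, the total would be 4, and the planned minimum of 3 could not occur in a completed q6h subject. All samples must also relate to one infusion, and the stop rule is a prohibition, not an order to keep dosing. Detailed procedures sit in laboratory and pharmacy manuals that are not in view.

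Much of this stands as evidence of intent. It does not amount to an instruction. The minimum is only an expected one, a fourth dose still lies within 3 to 6, and the same-infusion rule says which infusion to sample around, not whether the next may start.

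The safeguards are real too. Infusion and sampling times are recorded, individual plots use actual times, plasma means are also plotted by regimen, population PK can include the extra infusion, and there is no inferential testing. They limit the harm but do not correct the planned nominal-time summaries.

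A reader might infer that q6h subjects will be infused during sampling, or that the primary endpoints are compromised in general. The documents support neither. They leave the 6 h dose unaddressed, and ELF and the ratio are touched only in a q6h subject with a late BAL.

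**Conclusion.** The gap holds as a minor one. The timing overlap is certain from the stated schedule. Whether a site would actually give the 6 h dose is not known, and the manuals may settle it.

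If it is given, the effect on an individual plasma value is large (1.9 times at 7 h, 3.1 times at 8 h; 2.6 and 4.8 times at the assumed 2.0 h). The effect of one such subject on the 7 h arithmetic mean is modest: 5.5% with 18 subjects and 11% with 9. These figures rest on a one-compartment model, an on-time dose at 6 h and one affected subject.

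For a late BAL the ratio is bounded, not estimated. It would be wrong to read 0.52 as the expected result, because it requires ELF not to have responded at all, which no document supports. It would equally be wrong to read it as the floor, because a draw at 8 h or a shorter half-life takes the limit lower, to 0.21.

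**What to change.** In Protocol 3.3.1, 5.2 and Appendix 2, and in SAP 2.2 and 3.5, add: *The dose around which BAL and PK sampling is performed is the last dose; no further infusion starts until all BAL, plasma and urea samples have been collected.*

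As a back-up in SAP 8.4, exclude from every nominal-time summary and pooled plot, not only those at 7 h, any plasma or ELF sample drawn after a further infusion has started, together with its ratio. Keep these values in the listings.

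The cost is one sentence and one rule that uses times already recorded. The downside is that an occasional value is lost from a summary.
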